4.2. General Data Handling Conventions

4.2.1. Study Treatment Description

Randomized treatment groups will be displayed as show in the following table:

Data Displays for Reporting

Description	Order in TLF
Placebo	1
Vibegron 75mg	2
Overall	3

4.2.2. Reporting Conventions

General rules

In general, all collected safety data and any derived efficacy parameters from daily evening pain diary and daily bowel movement diary and PRO data will be presented in subject data listings, for all enrolled subjects. Listings will be ordered by treatment subject number, and assessment week or event date. The treatment group presented in listings will be based on the planned assignment, unless otherwise noted.

Summary tables will be provided for all randomized subjects. All demographic and baseline data will be presented by treatment arm and overall, unless otherwise specified. Efficacy, PRO and safety data will be presented by treatment arm only. In general, continuous variables will be summarized to include the population sample size (N), number of subjects with available data (n), arithmetic mean, SD, median, minimum, Q1, Q3 and maximum values. Categorical variables will be summarized by the population size (N), number of subjects with available data (n), number of subjects in each category, and the percentage of subjects in each category. Unless otherwise noted, the denominator to determine the percentage of subjects in each category will be based on the number of subjects with available data (n) in the analysis set of interest. Selective ordinal data may be summarized using both descriptive statistics and counts and percentages of subjects in each category, as appropriate.

The data analyses will be conducted using the SAS® System (SAS Institute Inc., Cary, NC) version 9.4 or above. The [REDACTED]’ standard operating procedures will be followed for the validation of all SAS programs and outputs.

Formats

Numeric data will be reported at the precision collected on the eCRF. The reported precision from non eCRF sources may be adjusted to a clinically interpretable number or decimal places.

Unscheduled Visits

Unscheduled visits will be assigned to a study visit using the all-inclusive windows defined in [Section 4.2.4](#). However, for by visit summaries, only the planned assessment time points will be summarized. Assessments at unscheduled visits will be included for “any time On-treatment” timepoints and in data listings, as well as algorithms to determine the maximum.

4.2.3. Premature Withdrawal and Missing Data

All data collected in the study database after the subject's early withdrawal of study treatment should be included in summary and analysis.

If any missing data are present in diary data for any reasons, no imputation will be applied to derive responder since the minimum compliance rules described in responder definition in [Section 4.3.1](#) accounted for missing diary entries. No explicit missing data imputation will be performed for change from baseline since a mixed model for repeated measures (MMRM) will be applied to change from baseline analysis. Missing items from the subject reported outcomes (PROs) will be handled according to the respective measure instructions as described in [Section 4.3.2](#).

In general, missing safety data will not be imputed and only observed values will be analyzed. Data of subjects who withdraw after the screening examination or are not treated will be only listed.

If the relationship of an AE record (“Relationship to investigational product” on AE CRF) is missing this AE will be considered “Probably Related” to the study treatment. If the AE intensity is missing every effort should be made to acquire the information from the investigator. “Severe” will be assigned to a missing intensity for reporting purpose

The general imputation rules of partial missing date for both AE and concomitant medication is detailed below:

Dates missing only the day of the month within a year will adhere to the following conventions:

- The missing day of onset date will be set to:
 - First day of the month that the event occurred, if the onset YYYY-MM is after the YYYY-MM of first double-blind treatment
 - The day of the first run-in treatment, if the onset YYYY-MM is the same as YYYY-MM of the first run-in treatment, but different from YYYY-MM of the first double-blind treatment
 - The day of the first double-blind study treatment, if the onset YYYY-MM is the same as YYYY-MM of the first double-blind treatment and the first single-blind treatment
 - The date of informed consent, if the onset YYYY-MM is before the YYYY-MM of the first single-blind treatment.
- The missing day of end date will be set to:
 - The last day of the month of the occurrence. If the subject died in the same month, then set the imputed date as the death date.

Dates missing both the day and month of the year will adhere to the following conventions:

- Missing day of onset date will be set to:
 - January 1 of the year of the onset, if the onset YYYY is after the YYYY of the first double-blind treatment
 - The date of the first run-in treatment, if the onset YYYY is the same as YYYY of the first run-in treatment, but different from YYYY of the first double-blind treatment
 - The date of the first double-blind treatment, if the onset YYYY is the same as YYYY of the first double-blind treatment
 - The date of informed consent, if the onset YYYY is before YYYY of the first run-in treatment
- The missing date of end date will be set to:
 - December 31 of the year of occurrence. If the subject died in the same year, then set the imputed date as the death date.

Missing items from the subject reported outcomes (PROs) will be handled according to the respective measure instructions as described in [Section 4.3.2](#).

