4.3.2. Reporting Questionnaire Scoring

4.3.3. Study Day and Duration

Study day is relative to the start date of the double-blind treatment. This is used to describe the relative time of an event or assessment happened during the study. The first day of the study is defined as the day a subject first receives either vibegron or placebo in the double-blind treatment period. This is expected to be the same day as the randomization as Day 1. There is no study Day 0 is defined in the study.

- For an event or assessment that occurred on or after the first dose of double-blind treatment date:

:

Study day = Date of event or examination – date of first double-blind study treatment + 1

- For an event or assessment that occurred prior to the first dose of double-blind treatment date:

Study day = Date of event or examination – date of first double-blind study treatment

Similarly, a duration between any two dates (such as AE duration) expressed in days will be calculated using the following conventions:

- Duration = Later date – earlier date + 1, if the earlier date is on or after the date of first dose of double-blind treatment
- Duration = Later date – earlier date, if the earlier date is prior to the date of first dose of double-blind treatment

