7.3. Adverse Events

AEs will be coded using MedDRA version 23.0. or later.

All reported AEs (whether treatment emergent or not) will be included in by-subject AE listings. Sorting will be by treatment subject, date of event, SOC, PT and then verbatim description.

An AE will be considered treatment emergent (TEAE) if it begins or worsens in severity after the first dose of the double-blind study treatment through 14 days after the last dose of study treatment. Partial AE start dates will be imputed as detailed in [Section 4.2.2](#)

Summary tables will be based on TEAEs. The incidence of TEAEs will be presented using counts and percentages of subjects with TEAEs and tabulated by SOC and PT. SOC will be sorted in descending frequency and PT within SOC will be sorted by descending frequency based on the incidence across subjects overall. If a subject has multiple occurrences (start and stop) of an event associated with a specific SOC or PT within a SOC, a subject will only be counted once in the incidence count for the SOC or PT within SOC respectively.

An overall summary table of AEs by treatment group will be presented detailing the number and percentage of subjects, and number of events for the following categories:

- At least one TEAE;
- At least one Treatment-Related TEAE;
- At least one Grade ≥ 3 TEAE (Mild = Grade 1, Moderate = Grade 2, Severe = Grade 3,

Life-Threatening = Grade 4, Death = Grade 5)

- At least one Grade ≥ 3 Treatment-Related TEAE;
- At least one Serious TEAE;
- At least one Serious Treatment-Related TEAE;
- At least one TEAE leading to Discontinuation from Study Medication;
- At least one TEAE of Special Interest;
- At least one Treatment-Related TEAE of Special Interest

Except for all TEAEs which will be summarized by SOC and PT, the incidence of all other TEAEs by PT will be presented for the following

- All TEAEs by SOC and PT;
 - Treatment-related TEAEs (i.e., possibly or probably related);
 - All TEAEs by PT, and maximum severity (where the maximum intensity per subject will be counted at each level of summarization);
- TEAES with Grade ≥ 3 ;

- Treatment-related TEAES with Grade ≥ 3 ;
- Serious TEAEs;
- Treatment-related serious TEAEs;
- Fatal TEAE;
- TEAEs leading to discontinuation from study treatment;
- TEAE of Special Interest;
- Treatment-related TEAE of Special Interest;
- Non-fatal serious TEAE;

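### SAP 4.2.3 never checks an imputed AE onset against a recorded end date, and one missing-day case has no rule

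*SAP*

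**What the plan says.** SAP 4.2.3 gives one set of partial-date rules for adverse events and concomitant medications. Day 1 below is the date of the first double-blind dose.

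If only the day of onset is missing:

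- Rule 1 uses: "First day of the month that the event occurred, if the onset YYYY-MM is after the YYYY-MM of first double-blind treatment".
- Rule 2 uses the first run-in day if the onset month is the run-in start month, "but different from YYYY-MM of the first double-blind treatment".
- Rule 3 uses Day 1, "if the onset YYYY-MM is the same as YYYY-MM of the first double-blind treatment and the first single-blind treatment".
- Rule 4 uses: "The date of informed consent, if the onset YYYY-MM is before the YYYY-MM of the first single-blind treatment".

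If day and month are both missing, the same-year rule uses: "The date of the first double-blind treatment, if the onset YYYY is the same as YYYY of the first double-blind treatment". It has no condition on the run-in year.

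A missing end day becomes: "The last day of the month of the occurrence", or the death date if the subject died in that month. No rule compares the imputed onset with the end date.

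Treatment-emergent status follows from the start date. SAP Table 1 puts an AE in the blinded treatment period if it starts on or after the first double-blind dose date and ends no later than 14 days after the last one. Protocol 9.4.3.1 also counts an onset on the first-dose date. SAP 7.3 words it as starting or worsening after the first double-blind dose. SAP 7.3 adds: "Partial AE start dates will be imputed as detailed in" Section 4.2.2, but the rules stand in 4.2.3.

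**The concern.** Placing an uncertain onset at the first dose is a reasonable cautious choice while the event could have begun on treatment. It is wrong once the record shows that the event was over before treatment began. Such records can exist: protocol 8.4.1 collects AEs from consent, so screening and run-in events are on file.

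A second weakness is that the four missing-day rules do not cover every order of months. An event that fits none of them has no imputed onset, and the programmer must then decide whether it is treatment-emergent.

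SAP 7.3 bases its AE summary tables on treatment-emergent events, so both faults reach them. Single records can matter in a trial of this size. Table 14.3.2.5 lists terms reported by at least 2% of the vibegron arm (2 of the planned 100 women), provided that the rate also exceeds placebo. For concomitant medications, a drug stopped before Day 1 with a year-only start in the Day 1 year would be given a Day 1 start and be counted as concomitant.

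**Working it through.** The plan states no figure on this point, so there is none to reproduce. The rules were applied literally.

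**1. End date ignored (illustrative dates).** Run-in starts 5 March and Day 1 is 19 March. An AE has onset in March with the day missing, and a recorded end of 10 March.

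- The onset month equals both first-dose months, so rule 3 gives 19 March.
- 19 − 10 = 9: the imputed onset is nine days after the recorded end.
- Table 1: the start (19 March) is not before the first double-blind dose, and the end (10 March) is not later than last dose + 14 days. Both conditions hold, so the event falls in the blinded treatment period.
- With only the year recorded and the same end date, the same-year rule also gives 19 March.

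**2. Coverage when only the day is missing.**

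| Onset month | Run-in and Day 1 in same month | Run-in started the month before Day 1 |
|---|---|---|
| Before run-in month | rule 4 | rule 4 |
| Run-in month | rule 3 | rule 2 |
| Day 1 month | rule 3 | **no rule** |
| After Day 1 month | rule 1 | rule 1 |

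Example of the empty cell: run-in from 25 February 2020, Day 1 on 10 March 2020, onset in March. The year-only rules have no such gap, because their Day 1 rule depends on the Day 1 year alone.

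**3. How often the months differ.** The run-in is 14 days (Day -14 to Day 1, no Day 0). The ± 4 day window at Visit 2 gives 10 to 18 days. Assume Day 1 dates are spread evenly over a 365-day year. With a run-in of L days, the months differ when Day 1 is on calendar day 1 to L, so the share is 12 × L / 365:

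- L = 10: 120 / 365 = 33%
- L = 14: 168 / 365 = 46%
- L = 18: 216 / 365 = 59%

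**4. Which onsets fall in the gap.** Assume onsets are also spread evenly over days.

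*Onsets during run-in, L = 14* (365 × 14 = 5,110 day combinations):

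- No rule: 12 × (0 + 1 + … + 13) = 12 × 91 = 1,092, or 21%.
- Rule 2: 12 × (1 + 2 + … + 14) = 12 × 105 = 1,260, or 25%.
- Rule 3: 5,110 − 1,092 − 1,260 = 2,758, or 54%.

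The no-rule share is 540 / 3,650 = 15% at 10 days and 1,836 / 6,570 = 28% at 18 days. It is the smallest of the three shares at each length.

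*Onsets on treatment within the Day 1 month.* Summing m(m + 1)/2 over the months, where m is the number of days in the month, gives 7 × 496 + 4 × 465 + 406 = 5,738 combinations. Those with no rule number 365 × L − 12 × L(L − 1)/2:

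- L = 14: 5,110 − 1,092 = 4,018, or 70%
- L = 10: 3,650 − 540 = 3,110, or 54%
- L = 18: 6,570 − 1,836 = 4,734, or 82.5%

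At 14 days the gap holds 4,018 on-treatment combinations against 1,092 from run-in, so it mostly concerns events that began on treatment.

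**The case against.** The case for leaving the text alone has force. Moving an uncertain onset to the first dose matches the cautious rules in the same section, where a missing relationship becomes probably related and a missing intensity becomes severe. The end-date fault needs a partial onset together with an end known to precede Day 1. If the end day is also missing in the Day 1 month, it becomes month-end and no contradiction arises. All AEs are listed with start, stop, onset period and treatment-emergent flag, so an impossible pair of dates would be visible. Blinded dry runs precede database lock, and SAP 7 plans no inferential safety testing.

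This limits the harm, but it does not supply the missing rule. Caution does not justify overriding a recorded end date.

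A reader might infer more than the documents support:

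- *That the uncovered case is the usual one for run-in events.* It is the least common of the three: 21%, against 54% under rule 3.
- *That the gap creates false treatment-emergent events.* It leaves status undefined. Since it mostly holds on-treatment onsets, the likelier harm is an event lost or classified ad hoc.
- *That run-in events are charged to vibegron.* The rules ignore treatment arm and apply equally to placebo. This is misclassification, with no shown bias toward either arm.
- *That 46% of AEs are affected.* That is the share of women whose run-in crosses a month. An affected AE also needs a missing day and an onset in the Day 1 month.
- *That the duration formula adds to the problem.* SAP 4.3.3 drops the extra day "if the earlier date is prior to the date of first dose of double-blind treatment", so a one-day run-in event lasts 0 days. No visible output reports AE duration, and treatment-emergent status does not depend on it.

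**Conclusion.** Two drafting faults stand. The first gives a wrong answer: an event known to have ended before Day 1 can be dated after its own end and counted as treatment-emergent. The second gives no answer for a case that the year-only rules handle.

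The number of events affected cannot be found from the documents, which give no count of partial dates; it is probably small. The percentages assume start dates and onsets spread evenly over the calendar, and describe exposure to the gap, not events misclassified.

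The first fault also depends on which definition governs. Under Table 1 and the protocol, an onset imputed to the Day 1 date counts. Under a strict reading of SAP 7.3 it might not, and then events correctly moved to Day 1 could drop out as well. That wording therefore has to be settled at the same time. The correction is worth making before unblinding because it is cheap and removes discretion from the AE tables.

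**What to change.** In SAP 4.2.3, for AEs and concomitant medications:

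1. Use the Day 1 date for a partial onset only if the end date is missing or on or after the first double-blind dose.
2. If the recorded end date is before that dose, use the first run-in dose date if it is on or before the end date, otherwise the consent date, and never a date later than the end date. Where the recorded month or year starts after the date so chosen, use its first day, so that the imputed onset agrees with what was recorded. Classify such an AE as not treatment-emergent.
3. Delete the condition on the single-blind month from rule 3, so that it matches the year-only rule and closes the gap.

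In SAP 7.3, count onsets on or after the first double-blind dose date, as in Table 1 and protocol 9.4.3.1, and correct the cross-reference for partial start dates from 4.2.2 to 4.2.3.

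The cost is a few words in the SAP and a few lines of derivation code. No data collection changes.

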4.2.4. Assessment Windows

4.2.4.1. Study Reporting Periods

Based on study design and variables under consideration, study time periods are defined as below.

Table 1: Definition of Study Reporting Periods

Analysis description	Analyzing Study Period	Start Date	End Date
General	Screening	Date of informed consent	Date of first run-in dose
	Run-in	Date of first run-in single-blind dose	Date of last run-in single-blind dose
	Blinded Treatment (Day 1 – Week 12)	Date of first double-blind dose	Date of last double-blind dose + 14
	Follow-up (up to Week 15)	Date of last dose + 14 days	Date of last contact
Adverse events	Screening	Start date \geq date of informed consent	End date $<$ date of first single-blind run-in dose
	Run-in	Start date \geq date of first single-blind run-in dose	End date \leq date of last single-blind run-in dose
	Blinded Treatment	Start date \geq date of first double-blind dose	End date \leq date of last double-blind dose + 14 days
	Follow-up	Start date $>$ date of last dose + 14 days	Date of last contact
Concomitant Medication	Prior medication	Start date $>$ date of first double-blind dose	

Analysis description	Analyzing Study Period	Start Date	End Date
	Concomitant mediation	Start date \geq date of first double-blind dose, or	End date \leq date of last double-blind dose + 14 days
		Start date $>$ date of first double-blind dose, but ongoing during double-blind treatment period	End date \leq date of last double-blind dose + 14 days
	Post medication	Start date $>$ date of last double-blind dose +14 days	
The date of last contact is the maximum date of study discontinuation, follow-up contact or the return of study medication. When lost to follow-up, the latest date of assessment/event in the database will be used as the last known date of the subject in study.			

4.2.4.2. Analysis Visiting Window

Analysis windows will be used for eDiary, safety (vitals and labs) as well as quality of life endpoints.

All measurements including the ones from the unscheduled visits that fall within the “Visit Window” will be used in the windowing algorithm to determine the analysis visit. Relative study day will be derived based on [Section 4.3.3](#). Note that the date of the first double-blind dose is Day 1 and the day before the date of the double-blind first dose is Day -1. Thus, there is no Day 0.

For the safety assessments and quality of life endpoints, if there are multiple values for in one window, the visit closest to the nominal day will be selected for assessing endpoints at a particular visit and for by-visit displays. If the visits are equally distant from the nominal day, then the earlier visit will be selected. All values will be stored in analysis datasets.

Check that all records slotted to a post-treatment visit are greater or equal to 15 days after the last dose date. Any post-treatment visit occurring less than 15 days after the last dose date should be re-slotted to an on-treatment visit using the corresponding relative day windows constructed for that parameter.

Table 1. For eDiary, the following analysis visit window slotting will be used to determine weekly assessments:

Analysis window label	Visit Window
Screening	NA
Run-in	NA
Baseline	[-7, -1]

Analysis window label	Visit Window
Week 1	[1, 7]
Week 2	[8, 14]
Week 3	[15, 21]
Week 4	[22, 28]
Week 5	[29, 35]
Week 6	[36, 42]
Week 7	[43, 49]
Week 8	[50, 56]
Week 9	[57, 63]
Week 10	[64, 70]
Week 11	[71, 77]
Week 12	[78, 84]
Follow-Up for Early Withdrawals	>Last dose date + 14
Follow-Up for Completers	>Last dose date + 14

Note: Only calculate the upper bound of last dose date + 14 if the relative study day of the last dose date is ≥ 71 days

Table 2: Analysis Visit Window Slotting for Safety Laboratory and Vitals

Analysis window label	Nominal visit	Nominal day	Visit Window
Screening	Visit 1	NA	NA
Run-in	Visit 2	NA	NA
Baseline ¹	Visit 3	1	NA
Week 2	Visit 4	15	[2, 22]
Week 4	Visit 5	29	[23, 42]
Week 8	Visit 6	57	[43, 70]
Week 12	Visit 7	85	[71, last dose date + 14,]
Follow-Up for Early Withdrawals	NA	NA	>Last dose date + 14
Follow-Up for Completers	NA	NA	>Last dose date + 14

¹ See [section 4.3.4](#) for definition of baseline

Note: Only calculate the upper bound of last dose date + 14 if the relative study day of the last dose date is ≥ 71 days

Table 3: Analysis Visit Window Slotting for ePRO assessments GIS and Additional Pain questions

Analysis window label	Nominal visit	Nominal day	Visit Window
Screening	Visit 1	NA	NA
Run-in	Visit 2	NA	NA
Baseline ¹	Visit 3	1	NA
Week 2	Visit 4	15	[2, 22]
Week 4	Visit 5	29	[23, 42]
Week 8	Visit 6	57	[43, 70]
Week 12	Visit 7	85	[71, last dose date + 14]
Follow-Up for Early Withdrawals	NA	NA	>Last dose date + 14
Follow-Up for Completers	NA	NA	>Last dose date + 14

¹ See [section 4.3.4](#) for definition of baseline

Note: Only calculate the upper bound of last dose date + 14 if the relative study day of the last dose date is ≥ 71 days

[figure not shown]

Table 5: Analysis Visit Window Slotting for Weekly Pain and Bowel Movement Diary

Analysis window label	Visit Window
Screening	NA
Run-in	NA
Baseline	[-7, 11]
Week 1	[1, 7]
Week 2	[8, 14]
Week 3	[15, 21]
Week 4	[22, 28]
Week 5	[29, 35]
Week 6	[36, 42]
Week 7	[43, 49]

Analysis window label	Visit Window
Week 8	[50, 56]
Week 9	[57, 63]
Week 10	[64, 70]
Week 11	[71, 77]
Week 12	[78, 84]

